5.18 Early Discontinuation

An individual subject is considered to undergo Early Discontinuation if the subject stops study participation before the Month 6 Phone Call.

An enrolled subject may voluntarily withdraw consent for further participation at any time before the Month 6 Phone Call. The Investigator will request (but cannot require) such subjects to provide the reason(s) for withdrawal of consent and to undergo an Early Discontinuation visit.

In addition, the Investigator, at his or her discretion, may withdraw a subject from further participation in the study. Criteria for withdrawal by the Investigator include:

- Noncompliance with the protocol
- Lost to follow-up – requires documentation of at least 3 unsuccessful attempts to contact the subject. Lost to follow-up will be determined after the date of the subject's projected last visit. Final attempt should be accompanied with a certified mail.
- Other reason(s) which, in the opinion of the Investigator, indicates that continued participation in the study is not in the best interest of the subject.

The Investigator or designee must report any early discontinuation for safety reasons to the Medical Monitor or designee within 24 hours of discontinuation. Additional information regarding ongoing AEs may be provided as a follow-up report.

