9.5.3 Unsolicited AEs

All the unsolicited AEs occurring during the study will be recorded, regardless of their assessment of relatedness by the Investigator.

The original verbatim terms used by Investigators to identify AEs will be mapped to preferred terms using the MedDRA dictionary. The unsolicited AEs will then be grouped by MedDRA preferred terms into frequency tables according to system organ class (SOC). All reported AEs, as well as AEs judged by the Investigator as at least possibly related to study vaccine, will be summarized by treatment group, according to SOC and preferred term within SOC. When an unsolicited AE occurs more than once for a subject, the maximum severity reported and strongest reported relationship to the treatment group will be counted.

Only TEAEs will be summarized as defined in [Section 7.1.1](#). The selection of unsolicited AEs and their assignment to time intervals will be done by day of onset and not by days ongoing/persisting.

Unsolicited AEs will be summarized by alphabetic SOC, and preferred term as follows:

- Any unsolicited TEAE
- Possibly or probably related unsolicited TEAEs
- SAEs
- Possibly or probably related SAE
- Unsolicited TEAE leading to withdrawal
- Any AE leading to death

Listings of all TEAEs will be provided by subject.

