6.2. Study Population

6.2.1. Subject Disposition

Subject disposition will be presented by treatment group and overall, including the number screened, the number of screen failures and the number randomized. The study disposition will also be presented along with the reasons for early study withdrawal.

The number of subjects in each analysis set will be presented on the Randomized Population by treatment group and overall.

The following by-subject listings will be presented.

- Study completion information, including the reason for premature study withdrawal
- Visit dates
- Inclusion in study Analysis Sets and reason for exclusion from the IEP
- Protocol deviations

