6.4.1.2. Unsolicited Adverse Events

An unsolicited AE is an AE that is spontaneously reported by the subject or discovered by the Investigator. SAEs, NOCIs and MAAEs would be recorded as part of the collection of unsolicited AEs as specified in the visit procedures. Unsolicited AEs are collected separately from solicited AEs.

Solicited AEs continuing beyond 7 days will be flagged using rules given in Section 5.2 and described in separate summaries as explained in Section 6.4.1.3.

The definition of a treatment emergent AE (TEAE) is an event that occurs after vaccination and within the 28 days after vaccination (i.e., excluding those after a subject has given informed consent, but before vaccination):

- Onset (days) = Start date of AE – Date of Study Vaccine Administration + 1
- An AE is a TEAE if Onset \geq 1 and Onset \leq 28

Adverse events are summarized by subject, therefore, in any tabulation, a subject contributes only once to the count for a given adverse event (SOC or preferred term).

Unsolicited AEs will be coded using the Medical Dictionary for Regulatory Activities (MedDRA) and will be summarized by decreasing frequency of SOC and preferred term within SOC in the control group, as follows:

- Any unsolicited TEAEs
- Possibly or probably related unsolicited TEAEs
- Unsolicited TEAEs leading to study withdrawal
- Any AE leading to death
- Any SAE within 6 months after the vaccination by maximum relationship to study treatment. This summary will include serious solicited AEs.
- Any NOCI within 6 months after the vaccination by maximum relationship to study treatment.
- Any MAAEs within 6 months after the vaccination by maximum relationship to study treatment.

Following by-subject Listings will be provided:

- Pre-vaccination AEs (non-emergent)
- All unsolicited TEAEs
- All post-vaccination SAEs, NOCIs and MAAEs

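### The only event-level summary of AEs leading to study withdrawal is limited to unsolicited events with onset Day 1 to 28, so withdrawals due to solicited reactions or later events are not shown by term or relatedness

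*SAP*

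**What the plan says.** SAP 6.4.1.2 lists the tables planned for unsolicited AEs. One concerns withdrawal: "Unsolicited TEAEs leading to study withdrawal". Protocol 9.5.3 lists the same item as "Unsolicited TEAE leading to withdrawal".

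Two definitions set its scope. The SAP counts onset as "Onset (days) = Start date of AE – Date of Study Vaccine Administration + 1" and then states "An AE is a TEAE if Onset \geq 1 and Onset \leq 28". It also separates the two kinds of event: "Unsolicited AEs are collected separately from solicited AEs".

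Withdrawal itself has no such limits. Protocol 5.18 says: "An individual subject is considered to undergo Early Discontinuation if the subject stops study participation before the Month 6 Phone Call".

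Other items in the same SAP list are wider. The SAE summary runs to 6 months, and the SAP adds: "This summary will include serious solicited AEs". The item on AEs leading to death carries neither the unsolicited nor the TEAE limit in its wording. The NOCI and MAAE summaries run to 6 months.

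Outside the AE section, SAP 6.2.1 plans: "The study disposition will also be presented along with the reasons for early study withdrawal". It also plans a by-subject listing of the reason.

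**The concern.** The primary objective is safety and tolerability at three dose levels. Leaving the study because of a reaction is a direct sign of poor tolerability, and after a single injection a solicited reaction is an obvious candidate cause. The one table that links AEs to withdrawal leaves those reactions out. It also leaves out events that begin during the follow-up period.

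The documents foresee both kinds of withdrawal. Protocol 6.2 sets out a discontinuation visit in the first week, with diary review. The SAP 6.4.1.1 duration rule provides for a solicited event still ongoing when the subject leaves. Protocol 5.18 asks for prompt reporting of discontinuations on safety grounds, without limiting this to unsolicited events or to the first 28 days.

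At stake is a table that shows fewer AE-related withdrawals in an arm than occurred. A reader comparing dose levels could take it as the full count.

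**Working it through.** This is a question of table scope, so the main check sets the planned outputs side by side.

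| Planned output | Place | Solicited reactions | Onset after Day 28 | Linked to withdrawal |
|---|---|---|---|---|
| Solicited AEs by term, day, severity, onset, duration | SAP 6.4.1.1 | Yes | No | No |
| Unsolicited TEAEs, all and related | SAP 6.4.1.2 | No, on SAP wording | No | No |
| Withdrawal item | SAP 6.4.1.2, Protocol 9.5.3 | No, on SAP wording | No | **Yes** |
| AEs leading to death | SAP 6.4.1.2 | Not excluded by its wording | Not excluded by its wording | No (fatal events only) |
| SAEs to 6 months | SAP 6.4.1.2 | Serious ones | Yes | No |
| NOCIs and MAAEs to 6 months | SAP 6.4.1.2 | Not stated | Yes | No |
| Continuing solicited, and combined | SAP 6.4.1.3 | Only those lasting past Day 7 | No | No |
| Disposition table and listing | SAP 6.2.1 | No event term planned | Whole study | Reason only |

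Only one row links an event term to withdrawal, and it is the narrowest in type of event and in time.

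**Window.** Input: the SAP onset formula.
- An event on the vaccination day has onset 0 + 1 = 1.
- An event 28 days after vaccination has onset 28 + 1 = 29. This exceeds 28, so it is not a TEAE.
- The SAP's verbal definition could be read to include that day. The difference is one day and does not affect the point.

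**Period outside the window.** Inputs: Month 6 at 180 days after Day 1 (Protocol 6.1.5), and 30.4375 days per month (SAP 5.2).
- Month 6 falls on Study Day 181, so the period is 181 − 28 = 153 days, and 153 / 30.4375 = 5.03 months.
- If Month 6 is read as Study Day 180: 180 − 28 = 152 days, and 152 / 30.4375 = 4.99 months.

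About five months of follow-up lie outside the item.

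**Solicited reactions.** There are eight terms (three local, five systemic).
- A reaction over within 7 days is only a diary event and cannot enter the item.
- A reaction lasting past Day 7 is also entered on the unsolicited page (SAP 5.2, Protocol 5.10). The SAP flags it and sends it to separate summaries. The combined table in SAP 6.4.1.3 adds such events to the unsolicited TEAEs, which implies that the latter term excludes them. On the Protocol's wording, some could enter.

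**Size per subject.** With 50 per arm (SAP 2.3), one omitted subject is 1 / 50 = 2 percentage points. The documents give no expected rate of AE-related withdrawal, so no total can be estimated.

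**The case against.** The strongest reply is that the information is reported elsewhere. Disposition is presented by treatment group with reasons and no time limit, and reasons are listed by subject. Solicited AEs are tabulated and listed. SAEs, NOCIs and MAAEs are tabulated to 6 months by relationship and listed. With about 50 subjects per arm, matching listings by hand is feasible. This largely stands: what is missing is a planned cross-tabulation, not the data. It does not remove the gap, because no planned output shows which event led to withdrawal, or its relatedness, for these subjects.

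It is also fair to say that withdrawal due to an AE is not a named endpoint, that one injection leaves no course of treatment to stop, and that the Protocol and SAP agree on the item. These points limit the importance.

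Three stronger readings are tempting, and the documents do not support them:
- *That withdrawals for AEs could not be recognised as such, because the grounds in Protocol 5.18 name no AE category.* That list is open, it covers withdrawal by the investigator, and the same section recognises discontinuation on safety grounds. The reason categories on the case report form are not in the documents.
- *That most of the relevant events are lost, because 153 of 181 days (85%) are outside the window.* This is calendar time, not a share of events. After Day 29 only SAEs, NOCIs and MAAEs are collected, by two phone calls.
- *That an arm would be reported as 0% instead of, say, 4%.* Two such withdrawals in 50 is an illustration with no rate behind it, and disposition would still show both subjects as withdrawn, with a reason.

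**Conclusion.** The gap is real and modest. The only event-level summary of AEs leading to study withdrawal omits two groups:
- withdrawals caused by solicited reactions: certainly those over within 7 days and, on the SAP's wording, also those that continue;
- withdrawals caused by SAEs, NOCIs or MAAEs with onset after Day 28.

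For both, the planned outputs give a withdrawal reason in disposition and the event in a separate table, with no link between them. No reason is given for the narrow scope, while neighbouring items were made wider, so an oversight is a plausible explanation.

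The size is 2 percentage points per omitted subject at 50 per arm, and the number of such subjects is probably small after a single dose. The conclusion rests on reading the SAP's unsolicited TEAEs as excluding flagged continuing solicited events. If they are included, the solicited part of the gap narrows to reactions over within 7 days; the late part is unchanged. This is a cheap improvement to reporting on the primary objective. It does not affect the validity of the other safety tables.

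**What to change.** In SAP 6.4.1.2, change the item to: *Any AE (solicited or unsolicited) with onset after vaccination through Month 6 leading to study withdrawal*, by system organ class and preferred term, relationship and treatment group, on the Safety Population. Keep the unsolicited-TEAE version as a subset, and add a by-subject listing. Align Protocol 9.5.3, or record the difference in SAP Section 7.

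Identify the events by reconciling the study completion reason with the AE and diary records before database lock. Do not assume that the action-taken entries in Protocol 7.5.2 hold the link. They cover the response to the AE and the action on study vaccine, and the documents do not show that either records study withdrawal.

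The cost is a change of wording, one revised table, one new listing and minor reconciliation work. The reported count of AE-related withdrawals may be slightly higher.

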2 OBJECTIVES AND ENDPOINTS

2.1 Primary

The primary objective is:

- To evaluate the safety and tolerability of a single injection of VAX-24 at three dose levels administered to healthy adults 65 years and older.

Safety and tolerability will be assessed by measuring the incidence of solicited local and systemic adverse events (AEs), unsolicited AEs, serious adverse events (SAEs), new onset of chronic illness (NOCI), and medically attended adverse events (MAAEs):

- Percentage of subjects reporting solicited local reactions within 7 days after vaccination (redness, swelling, and pain at injection site).
- Percentage of subjects reporting solicited systemic events within 7 days after vaccination (fever, headache, fatigue, muscle pain, and joint pain).
- Percentage of subjects reporting unsolicited AEs within 1 month after vaccination.
- Percentage of subjects reporting SAEs and NOCI within 6 months after vaccination.
- Percentage of subjects reporting AEs with a new onset or a worsening of a condition that prompts the subject to seek unplanned medical advice at a physician's office, urgent care center, or Emergency Department

[figure not shown]

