5.11 Unsolicited Adverse Events

Unsolicited AEs (any AEs not listed in the diary) will be collected for this study. Details regarding definitions, evaluation, reporting periods, and documentation are outlined in [Section 7](#).

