6.1.3 Day 8 (+3 days)

The following procedures will take place at this visit:

- Review of diary data with the subject; Investigator's assessment of severity and relationship to study vaccine
- Review of concomitant medications
- AE (solicited and unsolicited) and SAE evaluation

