3.2. Safety Variables

Safety assessments performed during the study included solicited AE up to Day 8 and monitoring of unsolicited adverse events including NOCI and MAAE, physical examinations, measurement of vital signs.

The primary safety endpoints are:

- Percentage of subjects reporting solicited local reactions within 7 days after vaccination (redness, swelling, and pain at injection site).
- Percentage of subjects reporting solicited systemic events within 7 days after vaccination (fever, headache, fatigue, muscle pain, and joint pain).
- Percentage of subjects reporting unsolicited AEs within 1 month after vaccination.
- Percentage of subjects reporting SAEs within 6 months after vaccination.
- Percentage of subjects reporting NOCIs within 6 months after vaccination.
- Percentage of subjects reporting MAAEs within 6 months after vaccination.

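### The SAP does not say whether the MAAE endpoint counts medically attended solicited reactions; read literally, it leaves out those confined to Days 1–7

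*SAP*

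**What the plan says.** **Endpoint definition.** Protocol 2.1 lists as a primary endpoint the "Percentage of subjects reporting AEs with a new onset or a worsening of a condition that prompts the subject to seek unplanned medical advice". The settings it names are a doctor's office, urgent care or emergency department. SAP 3.2 keeps it as "Percentage of subjects reporting MAAEs within 6 months after vaccination". Neither limits the endpoint to unsolicited events, and Protocol 7.1.2 makes clear that a solicited event is an AE.

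**Recording.** SAP 6.4.1.2 says that "SAEs, NOCIs and MAAEs would be recorded as part of the collection of unsolicited AEs as specified in the visit procedures", and adds that unsolicited AEs are collected separately from solicited ones. Protocol 5.11 gives the scope of unsolicited events: "Unsolicited AEs (any AEs not listed in the diary) will be collected for this study".

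**Tabulation.** The summary list in SAP 6.4.1.2 is introduced as a summary of unsolicited AEs. Its SAE line carries a rider, "This summary will include serious solicited AEs". Its MAAE line, "Any MAAEs within 6 months after the vaccination by maximum relationship to study treatment", has none.

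**Solicited events.** SAP 6.4.1.1 tabulates diary events from Day 1 to Day 7 by severity, day, onset and duration. Medical attendance is not among the listed summaries.

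**The concern.** The endpoint definition and the analysis rule appear to cover different sets of events. Suppose a subject visits urgent care on Day 3 for fever or arm swelling that resolves by Day 7. That subject meets the protocol's MAAE definition. The event, however, belongs to the diary, and the MAAE table is built from the unsolicited records.

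At stake is a primary safety endpoint in a study that compares three dose levels with PCV20 and whose sample size rests on the safety objective (SAP 2.2). If care-seeking for solicited reactions rises with reactogenicity, the omission would be largest in the most reactogenic arm. The documents give no data on whether it does. If sites differ in whether they re-enter such events on the unsolicited page, the count would also depend on site practice.

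**Working it through.** The documents give no MAAE rate, event count or power for this endpoint, so there is no planned figure to reproduce. The check is mainly a comparison of texts.

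**Step 1. Can a Day 1–7 solicited reaction reach the unsolicited records?**
- Protocol 5.11 confines unsolicited AEs to events not listed in the diary.
- Protocol 5.10 and 7.5.1 give two routes by which a solicited term enters those records: it occurs outside the 7-day window, or it continues past it.
- Neither document says that a reaction inside the window is re-entered because it was medically attended.

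**Step 2. What happens to reactions that continue past Day 7?** They are entered on the unsolicited page and flagged (SAP 5.2), then described in the separate summaries of SAP 6.4.1.3. None of those is an MAAE table. Whether these events also enter the MAAE table is not settled.

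**Step 3. Compare the two lines in the same list.**

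| Line in SAP 6.4.1.2 | Window | Solicited events added in words? |
|---|---|---|
| SAE | 6 months | Yes |
| MAAE | 6 months | No |

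A programmer following the list as written would add solicited events to the first table and not to the second.

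**Step 4. Is medical attendance captured early?** The visit lists name an MAAE evaluation only at the Month 3 and Month 6 calls (Protocol 6.1.5). Day 8 lists "AE (solicited and unsolicited) and SAE evaluation" and a diary review. Protocol 5.10 adds that staff review the action taken for the event, and Protocol 7.5.2 requires action taken to be documented for all AEs. Relevant information may therefore exist, but no rule carries it into the MAAE count.

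**Step 5. Size per missed subject.** Arm size is 200/4 = 50, as in SAP 2.3. A subject whose only medically attended event is a Day 1–7 solicited reaction moves the arm's percentage by 1/50 = 2.0 points. Two examples with two such subjects and assumed counts (exact 95% limits):
- 0/50 = 0% (0 to 7.1%) would become 2/50 = 4% (0.5 to 13.7%).
- 5/50 = 10% (3.3 to 21.8%) would become 7/50 = 14% (5.8 to 26.7%).

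**Step 6. How many might be missed?** Let q be the proportion of subjects of this kind. It is an assumption. The expected number missed per arm is 50q, and the chance of at least one among the 3 × 50 = 150 VAX-24 subjects is 1 − (1 − q)^150.

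| Assumed q | Expected missed per arm | Chance of at least one in 150 |
|---|---|---|
| 0.5% | 0.25 | 53% |
| 1% | 0.5 | 78% |
| 2% | 1 | 95% |
| 4% | 2 | 99.8% |

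These figures apply only on the literal reading, with no re-entry by sites.

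**The case against.** The strongest reply is that no sentence excludes these events. In the SAP 6.4.1.2 list, the first three lines carry the word unsolicited; the death, SAE, NOCI and MAAE lines do not. The recording sentence can be read as a routing rule that sends every MAAE to the unsolicited page, and it covers SAEs too, which Protocol 7.1.4 says may be solicited. The line for AEs leading to death also lacks a rider, yet nobody would drop a death after a solicited reaction. The CRF completion guidelines, which are not among these documents, may settle the matter.

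This stands as far as it shows that the exclusion is structural and that another reading is possible. It does not remove the problem. Two reasonable readings of a primary endpoint give different counts, and the rider on the SAE line favours the narrower one.

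A reader might go further in three ways that the documents do not support:
- **That the MAAE endpoint is certain to be under-counted.** That depends on how sites enter these events and on a rate that is not given.
- **That the Day 8 review looks only at severity and relationship.** Protocol 5.10 also has staff review the action taken, and Protocol 5.12 collects medications and procedures associated with solicited AEs through Day 29.
- **That a real difference between arms would be hidden.** Any such example needs invented rates. Take 6/50 against 4/50, a difference of 4 points. The standard error is √(0.12×0.88/50 + 0.08×0.92/50) = 0.060, so the approximate 95% interval is −8 to +16 points. A difference of that size could not be interpreted in any case.

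Nor does the reaction vanish: it counts in the solicited primary endpoints, and in the SAE table if serious.

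**Conclusion.** The concern holds in a limited form. The MAAE endpoint is defined over all AEs, but the only rule for tabulating it sits among unsolicited AE summaries and, unlike the SAE rule, does not bring in solicited events. On the literal reading, medically attended solicited reactions confined to Days 1–7 are left out. Because this is implied and not stated, inconsistent handling is as much a risk as uniform omission.

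The loss is to the MAAE count alone, at 2 percentage points per missed subject with 50 per arm. The number missed cannot be derived from the documents, and the range in the working rests wholly on assumed rates. No formal test is affected, since the sample size is not set by hypothesis testing. The gap is worth closing because the endpoint is primary and the correction is cheap.

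**What to change.** **SAP 6.4.1.2, MAAE line.** Add: *This summary will include medically attended solicited AEs.* This matches the SAE line. As worded it also covers solicited AEs that continue past Day 7, which the SAP now leaves open.

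**Identification rule.** State one of the following:
- medically attended solicited AEs are identified from the action-taken information already reviewed at Day 8 (Protocol 5.10, 7.5.2), provided that it records whether unplanned medical advice was sought; or
- sites record on the AE page any Day 1–7 solicited AE for which unplanned medical advice was sought, with a flag so that it does not also enter the unsolicited TEAE tables.

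If the exclusion is intended, say so and reconcile it with Protocol 2.1 and SAP 3.2.

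**Cost.** One SAP sentence, a small data-capture step and some programming. The programming includes MedDRA terms for up to eight solicited event types where these are not already coded, because the table is by system organ class and preferred term. MAAE percentages may be slightly higher than under the literal reading.
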